#### *Anti-insulin antibody response*

The number and percentage of patients will be provided by treatment group for each of the following categories:

- Patients with treatment-induced AIAs,
- Patients with treatment-boosted AIAs,
- Patients with treatment-emergent AIA (AIA incidence),
- Patients without treatment-emergent AIA,
- Patients with pre-existing AIAs or treatment-induced AIAs (AIA prevalence).

For exploratory purposes, the difference between the switching arm and the non-switching arm in the percentage of patients with treatment-emergent AIAs (AIA incidence) will be provided with associated 2-sided 90% CI. Patients with inconclusive results will not be part of the analysis. Results will be obtained by fitting a binomial regression model with an identity-link function. The model will include fixed categorical effects for treatment and the randomization stratum of screening HbA1c (<8%, ≥8%). If the model does not converge (e.g., due to sparse data), randomization strata may be removed from the model. The risks within each treatment group and risk difference will be provided with their 90% CIs using the adjusted LS mean estimates of the treatment effect.

For patients with treatment-induced and treatment-boosted AIAs, the peak titer will be described using median, Q1 and Q3.

The number and percentage of patients with treatment-induced, treatment-boosted and treatment-emergent AIAs will also be presented by visit in each treatment group using tables and/or graphs.

Boxplots of the peak AIA titer will be presented by treatment group and according to the treatment-emergent AIA status (Yes, No). These graphs will be used to identify AIA ‘outliers’, defined as peak AIA titers higher than the boxplot upper whiskers (ie, higher than 1.5 times the interquartile range above the third quartile).

A listing with inconclusive patients will be provided.

### ***Anti-insulin aspart antibody data by visit***

The number and percentage of patients with anti-SAR341402/NovoLog antibody positive and antibody negative samples will be summarized by treatment group at each visit. The number and percentage of patients with anti-SAR341402/NovoLog antibody positive sample will be displayed graphically by visit.

On the group of patients with anti-SAR341402/NovoLog antibody positive sample at a given visit, anti-SAR341402/NovoLog antibody titers will be summarized (using descriptive statistics by number (N), median, Q1, Q3, variation coefficient, minimum, maximum, geometric mean, SD, and 95% CI), and the number and percentage of patients with cross-reactivity to human insulin will be provided.

Boxplots of AIA titers will be presented at each visit.

The above by-visit summaries will be performed on the overall AIA population and for patients with treatment-emergent AIAs.

### ***Subgroup analyses***

Exploratory analyses will be performed by the subgroups defined by the Anti-SAR341402/NovoLog antibody status at baseline (Positive, Negative), and by COVID-19 impact (Non-impacted, Impacted; see subgroup definition in [Section 2.2](#)). The second subgroup analysis will be performed only if the number of patients is sufficient. Further subgroup analyses may be performed if deemed necessary for interpretation of results.

### ***Relationship between immunogenicity endpoints and efficacy/safety assessments***

Subgroup analyses and scatterplots will be conducted to assess the relationship between immunogenicity endpoints and efficacy/safety assessments.

The following safety/efficacy assessments will be summarized by treatment-emergent AIA (Yes, No) and for each treatment group:

- Hypoglycemia (any, severe, documented symptomatic): the proportion of patients with at least one event will be compared between treatment groups using the same statistical model as described in [Section 2.4.5.1](#) for hypoglycemia subgroup analyses.
- TEAEs: descriptive statistics presented by primary SOC and PTs, showing number (%) of patients with at least one TEAE, sorted by SOC internationally agreed order and decreasing incidence of PTs according to all TEAE summary within SOC.
- Serious TEAEs: descriptive statistics by primary SOC and PTs, showing number (%) of patients sorted by SOC internationally agreed order and decreasing incidence of PTs according to all TEAE summary within SOC.
- Injection site and hypersensitivity reactions: descriptive statistics by PT, showing number (%) of patients sorted by decreasing incidence of PT in the switching group.

- Efficacy endpoint (change from baseline to Week 16 in HbA1c): descriptive statistics by visit.
- Change in daily insulin doses (basal, mealtime, total) as defined in [Section 2.4.3](#): descriptive statistics by visit.

The relationship between the AIA titer and the efficacy and safety assessments will be explored using scatter-plots of the peak AIA titer versus the parameters below for patients from the AIA population with titer available:

- Rate per year of treatment-emergent hypoglycemia during the on-treatment period (severe hypoglycemia, documented symptomatic  $< 3.0 \text{ mol/L [54 mg/dL]}$ )
- Presence/absence of treatment-emergent hypersensitivity reactions during the on-treatment period
- Presence/absence of treatment-emergent injection site reactions during the on-treatment period
- Efficacy endpoint (change from baseline to Week 16 in HbA1c)
- Change in daily insulin doses (U/kg) from baseline to Week 16

The scatterplots will also be presented separately for patients with treatment-emergent AIAs.

Listings of baseline characteristics, insulin doses, HbA1c, hypoglycemia, hypersensitivity reactions, and injection site reactions will be provided for patients with treatment-emergent AIAs and high AIA titers (AIA ‘outliers’ as defined above).

Listings of anti-insulin aspart antibody, insulin doses, and HbA1c data will be provided for patients with treatment-emergent AIAs and HbA1c change from baseline  $> 1\%$  at Week 16.

A listing of patients with treatment-emergent AIA at end of treatment and potential effects on glycemic control will be provided with the result of adjudication by the ARAC diabetologist (including AIA-mediation and potential need for AIA post-study follow-up).

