### 3 OBJECTIVES AND ENDPOINTS

**Table 2 - Objectives and endpoints**

Objectives	Endpoints
Primary	
To demonstrate similarity in pharmacokinetics (PK) of SAR341402 and NovoLog after 4x4-week periods of alternating administration of SAR341402 and NovoLog compared to 16-week continuous use of NovoLog in participants with Type 1 diabetes mellitus (T1DM) also using insulin glargine	AUC last , AUC, and C max following injection of a predefined, fixed dose of SAR341402 or NovoLog (0.15 U/kg) at Week 16
Secondary	
To compare the effects of alternating administration of SAR341402 and NovoLog with continuous use of NovoLog on immunogenicity	Number of participants with treatment-emergent anti-Insulin aspart antibodies (AIAs) during the 16-week treatment period
To evaluate the safety of alternating administration of SAR341402 and NovoLog versus continuous use of NovoLog	Safety evaluations, which will include evaluation of the following (for the 16-week treatment period): 
 
• Number of participants with at least one hypoglycemic event 
 
- Number of hypoglycemic events per participant-year
 
- Number of participants with adverse events (AEs) (see Section 8.3)
 
 
 

To compare other PK parameters between the two treatment arms (alternating administration of SAR341402 and NovoLog and continuous use of NovoLog)	Time to C max (T max ) following injection of a predefined, fixed dose of SAR341402 or NovoLog (0.15 U/kg) at Week 16
Tertiary/exploratory	
To compare the effects of alternating administration of SAR341402 and NovoLog with continuous use of NovoLog on insulin dose	Change in Insulin dose (basal, meal-time [SAR341402 or NovoLog], total) from baseline to Week 16
To compare the effects of alternating administration of SAR341402 and NovoLog with continuous use of NovoLog on glycemic control	Change from baseline to Week 16 in HbA1c Change from baseline to Week 16 in FPG
To compare clinical effects of treatment-emergent AIAs on glycemic control, insulin dose and safety	Clinical effects of AIAs on efficacy (HbA1c), insulin dose and safety (hypoglycemia, hypersensitivity reactions, injection site reactions)

Objectives	Endpoints

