To compare the effects of alternating administration of SAR341402 and NovoLog with continuous use of NovoLog on additional immunogenicity parameters	
Number of participants with treatment-induced AIA (among the participants AIA-negative or missing at baseline) (during the 16-week treatment period)
 
Number of participants with treatment-boosted AIA (among the participants AIA-positive at baseline) (during the 16-week treatment period)
 
Number of participants by AIA status (positive/negative) at baseline, Week 8, Week 12 and Week 16
 
Anti-Insulin aspart antibody titer at baseline, Week 8, Week 12 and Week 16
 
Number of participants by AIA cross-reactivity to human insulin at baseline, Week 8, Week 12 and Week 16
 
Number of participants by anti-insulin aspart neutralizing antibody status (positive/negative) at baseline, Week 8, Week 12 and Week 16

To compare clinical effects of treatment-emergent neutralizing antibodies on glycemic control and insulin dose	Clinical effects of anti-insulin aspart neutralizing antibodies on efficacy (HbA1c) and insulin dose

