### **2.1.4 Immunogenicity variables**

As per protocol, only the number of patients with treatment-emergent anti-insulin aspart antibodies (AIA) during the 16-week treatment period is secondary. All other immunogenicity endpoints are tertiary/exploratory.

If a patient discontinues the treatment prematurely, the process described in [Section 2.5.1](#) will be applied to retrieve immunogenicity assessments performed at the end of treatment visit (Visit 8000).

AIA measurements will be performed in a blinded fashion at a central laboratory (see study flowchart in Section 1.3 of the protocol) using a validated anti-insulin aspart antibody binding assay methodology. Only AIA results from samples collected during the on-treatment period and at least 8 hours after the last administration of mealtime insulin will be taken into account in the analysis.

Anti-insulin aspart antibodies evaluation will consist of:

- Anti-SAR341402/ NovoLog antibody positive/negative status
- Anti-SAR341402/ NovoLog antibody titer
- Cross-reactivity to human insulin positive/negative status

The following definitions will be used to identify patients with a change in AIA response during the on-treatment period (see [Section 2.1.4](#) (1) :

- **Patients with treatment-induced AIAs** will be defined as patients with AIAs that developed de novo (seroconversion) following the IMP administration (ie, patients with at least one positive AIA sample at any time during the on-treatment period, in those patients without pre-existing AIA or with missing sample at baseline).
- **Patients with treatment-boosted AIAs** will be defined as patients AIA positive at baseline that were boosted to a significant higher titer following the IMP administration (ie, patients with at least one AIA sample with at least a 4-fold increase in titers compared to baseline value at any time during the on-treatment period, in those patients with preexisting AIA). The 4-fold increase in titer corresponds to an increase of two dilution steps within the titration experiment. A single dilution difference (2-fold titer increase) is within the expected imprecision of the titration method and is therefore not considered a relevant change.

Patients with treatment-emergent AIA (Yes, No, Inconclusive) will be derived as follows:

- Patients with treatment-emergent AIAs (AIA incidence) will be defined as patients with treatment-induced or treatment-boosted AIAs.

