### ***Safety observation period***

The observation period for safety data will be divided into 3 main segments:

- The **pre-treatment period** is defined as the time from informed consent up to the time of the first injection of IMP.
- The **on-treatment period** is defined as the time from the first injection of IMP up to the last injection of IMP + 1 day (included).
- The **post-treatment period** is defined as the time from the last injection of IMP + 2 days (included).

Analyses will focus on safety observations during the on-treatment period.

The **on-study observation period** is defined as the time from first injection of IMP until the end of the study (defined as the date of end of participation).

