#### ***Adverse event observation period***

The AE observations will be classified per the observation periods of safety data as defined in [Section 2.1.5](#) :

- **Pre-treatment AEs** are AEs that developed or worsened or became serious during the pre-treatment period.
- **Treatment-emergent AEs (TEAEs)** are AEs that developed or worsened or became serious during the on-treatment period.
- **Post-treatment AEs** are AEs that developed or worsened or became serious during the post-treatment period.

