#### **2.4.5.1 Analyses of Hypoglycemia**

All analyses of hypoglycemia will be performed on the safety population, using events occurring during the on-treatment period (as defined in [Section 2.1.5](#)).

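### Event summaries by treatment-emergent antibody status place events from before the antibody response in the Yes group; add a supplement that splits follow-up at the first qualifying sample

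*SAP*

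**What the plan says.** Protocol Table 2 (Objectives and endpoints) has a tertiary objective on the clinical effects of treatment-emergent AIA on glycemic control, insulin dose and safety. Safety here means hypoglycemia, hypersensitivity reactions and injection site reactions.

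- **Status.** SAP 2.1.4 gives each participant one status for the whole study. Treatment-induced means "patients with at least one positive AIA sample at any time during the on-treatment period", among those negative or missing at baseline. Treatment-boosted means "patients AIA positive at baseline that were boosted to a significant higher titer following the IMP administration", that is, at least a 4-fold rise. Either one makes the participant a Yes.
- **Sampling.** Table 2 lists "Anti-Insulin aspart antibody titer at baseline, Week 8, Week 12 and Week 16". Status is assessed at the same four times.
- **Analysis.** SAP 2.4.6.1 states: "The following safety/efficacy assessments will be summarized by treatment-emergent AIA (Yes, No) and for each treatment group". The proportion with at least one hypoglycemia is compared between arms with the logistic subgroup model of SAP 2.4.5.1. TEAEs, serious TEAEs and the two reaction types are n (%) tables. HbA1c and insulin dose changes are described by visit.
- **Event window.** Under SAP 2.1.5 the on-treatment period starts at the first IMP injection and ends one day after the last. Hypoglycemia is analysed "using events occurring during the on-treatment period". TEAEs "are AEs that developed or worsened or became serious during the on-treatment period". The peak-titer scatterplots use the same window.

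No section of either document splits follow-up at the first qualifying sample, restricts events to the time after it, or treats AIA status as time-dependent.

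**The concern.** The flag looks forward and the event count looks back. A participant who does not qualify at Weeks 8 and 12 and then qualifies at Week 16 carries every event from Day 1 into the Yes group, although the participant's own samples show no response for the first 12 weeks. Those events cannot be a consequence of a response that had not yet been seen.

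The at-least-one-event outcome has a further weakness. A single event before the response already makes the participant a case, and events after the response then add nothing.

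What is at stake is how informative the safety part of the tertiary AIA objective will be. A reader comparing Yes with No will take the difference as a description of what antibodies do, although part of the Yes follow-up predates them.

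**Working it through.** **Plan's own figure.** There is none to reproduce. The documents give no expected AIA incidence, no distribution of onset times and no event rates. The only sized analysis is the primary PK comparison, which this point does not touch.

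**Inputs from the documents.** Samples at baseline and Weeks 8, 12 and 16 (Protocol Table 2); a 16-week on-treatment period (Protocol 4.1); the Week 16 assessments may be delayed to about Week 24 because of COVID-19 (SAP 1.4).

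**Step 1: share of counted time before the response.** Lower bound = week of last non-qualifying sample / length of period. Upper bound = week of first qualifying sample / length of period.

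| Last non-qualifying | First qualifying | 16-week period | Final visit at Week 24 |
|---|---|---|---|
| Baseline | Week 8 | 0/16 to 8/16 = 0 to 50% | 0/24 to 8/24 = 0 to 33% |
| Week 8 | Week 12 | 8/16 to 12/16 = 50 to 75% | 8/24 to 12/24 = 33 to 50% |
| Week 12 | Final visit | 12/16 to 16/16 = 75 to 100% | 12/24 to 24/24 = 50 to 100% |

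In the first row no sample lies between baseline and Week 8, so the true share cannot be observed.

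**Step 2: effect on a rate contrast (assumptions).** Suppose event rates are constant and the rate before the response equals the No-group rate. With pre-response share f and true post-response rate ratio RR, the whole-period ratio is f + (1 − f) × RR.

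- RR 2, f 0.50: 0.50 + 0.50 × 2 = 1.50. With f 0.75: 0.75 + 0.25 × 2 = 1.25.
- RR 1.5: 1.25 and 1.125. RR 3: 2.0 and 1.5.

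**Step 3: effect on the at-least-one-event scale (assumptions).** Take a 20% risk in the No group, RR 2 and Poisson counts. The No mean is −ln(0.8) = 0.223 and its odds are 0.25.

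- f 0.50: Yes mean 0.223 × 1.50 = 0.335, risk 28.5%, odds ratio 1.59.
- f 0.75: Yes mean 0.223 × 1.25 = 0.279, risk 24.3%, odds ratio 1.29.
- Both groups counted only over the post-response window: 2.12 and 2.06.

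**Step 4: dependence on the onset mix (assumptions).** Use the lower-bound shares and RR 2.

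- All first qualify at Week 8: f = 0, ratio 2.0.
- Split 80/10/10 over Weeks 8, 12 and 16: f = 0.1 × 0.50 + 0.1 × 0.75 = 0.125, ratio 1.88.
- Equal thirds: f = (0 + 0.50 + 0.75)/3 = 0.417, ratio 1.58.

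**Step 5: a bias in the other direction (assumptions).** With no antibody effect, a 20% risk over 16 weeks and 10% of the No group stopping at Week 6, the No risk is 0.9 × 0.20 + 0.1 × (1 − e^(−0.223 × 6/16)) = 18.8%. The Yes/No odds ratio is then 1.08. With 20% stopping it is 1.17.

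**The case against.** The strongest reply is that no Yes-versus-No rate ratio is planned. The hypoglycemia model compares arms within AIA subgroups, the reactions are n (%) tables, and rates appear only in scatterplots. SAP 2.4.6.1 calls the immunogenicity analyses descriptive, without formal testing. This stands. The ratios above illustrate what a reader would see when comparing the columns; they are not distortions of a planned estimate.

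The second reply concerns timing. Protocol 4.2 expects antibodies about 2 weeks after first exposure, and SAR341402 starts at Week 4 in the switching arm, so most responses might be caught at Week 8. That is plausible. However, the same section expects an earlier response on re-exposure, and SAR341402 is resumed at Week 12, so a response triggered then would first show at Week 16. The documents do not settle the mix.

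Third, treatment-boosted participants are antibody-positive from baseline, so their early time is pre-boost rather than pre-antibody. Where the baseline sample is missing, early status is unknown. Both limits stand.

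Fourth, the SAP already plans AIA incidence by visit, event listings for titer outliers, and adjudicated AIA-mediation for glycemic effects. These help with individual cases, but they do not link event dates to sample dates across the Yes group and do not change the summaries.

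A reader might infer that some fixed fraction, such as the 42% from equal thirds, of Yes time precedes the response, or that the plan hides an antibody effect. The documents support neither. Any fraction depends on an onset mix that they do not give. Attenuation requires equal pre-response and No-group rates, and Step 5 shows that unequal follow-up can act the other way.

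**Conclusion.** The point holds as a limited one. The SAP applies an ever/never AIA flag to events counted from the first injection, so events from before the response fall in the Yes group.

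The Step 1 shares follow from the visit schedule. The Yes/No contrast is diluted if pre-response rates equal No-group rates, but its actual size is unknown and the net direction is not certain.

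The point concerns the event summaries and the event-based scatterplots. HbA1c and insulin dose are changes described by visit and do not share the problem. The analysis is tertiary and descriptive; the primary PK conclusion and AIA incidence are unaffected. This is a worthwhile improvement, not a flaw that threatens the trial.

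**What to change.** Keep the ever/never tables and the planned arm-by-AIA model. In SAP 2.4.6.1 add, for event outcomes only:

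1. A table of hypoglycemia, injection site reactions and hypersensitivity reactions by AIA status at event onset.
2. Event rates per patient-year with each participant's time split at the first qualifying sample: the first positive for treatment-induced, the first 4-fold rise for treatment-boosted. Earlier time counts as not yet emergent. Time after that sample stays emergent, so transient responders are still represented.
3. A sensitivity analysis dating onset at the last non-qualifying sample before the first qualifying one. Together with item 2 this brackets the unknown onset.
4. Separate display of induced and boosted participants, with missing-baseline participants flagged.

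Use actual sample dates for the split, because SAP 2.5.3 re-allocates premature end-of-treatment samples to a later scheduled visit.

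The cost is SAP wording and programming on dates already collected. Two limits remain. Onset is known only to within the sampling interval. Emergent time falls later in the study, so antibody status is partly confounded with time on treatment. The added output should therefore be labelled descriptive.

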##### ***Incidence of patients with at least one hypoglycemia***

- Incidence of patients with at least one hypoglycemia will be presented by treatment group for any hypoglycemia and for each hypoglycemia category (as described in [Section 2.1.5.1](#)). Non classified hypoglycemia will be displayed.
- For any hypoglycemia, severe and documented symptomatic hypoglycemia category, incidence of patients with at least one hypoglycemia will be compared for the switching arm versus the non-switching arm using a logistic regression method. The model will include fixed-effect terms for treatment group and the randomization stratum of screening HbA1c (<8%, ≥8). If the logistic model does not converge (e.g., due to sparse data), the randomization stratum may be removed from the model. Odds-ratios and 95% CIs will be displayed using forest plots.
- The number (%) of patients with at least one hypoglycemia leading to permanent IMP discontinuation will be provided by treatment group.
- Incidence of patients with at least one severe hypoglycemia with neuroglycopenic symptoms and/or SMPG <2.8 mmol/L (50 mg/dL) will be summarized.
- If the number of patients impacted by COVID-19 is sufficient, the incidence of patients with at least one hypoglycemia (any, severe, documented symptomatic) will also be

presented by subgroup of COVID-19 impact (Non-impacted, Impacted) (see definition [Section 2.2](#)) and compared between treatment groups using a similar logistic regression model as described above, with added fixed-effect terms for the subgroup and the subgroup-by-treatment interaction. Odds-ratios and 95% CIs will be presented across subgroups using forest plots. The significance level of the subgroup-by-treatment interaction will also be provided for descriptive purpose.

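### For the antibody objective, the SAP models hypoglycemia as arm versus arm within a post-randomization AIA grouping and names no AIA Yes-versus-No estimate

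*SAP*

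**What the plan says.** Protocol Table 2 lists, as tertiary/exploratory, "To compare clinical effects of treatment-emergent AIAs on glycemic control, insulin dose and safety". Protocol 3.1 adds that a possible effect of AIAs on hypoglycemia will be assessed.

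SAP 2.4.6.1, under the heading on the relationship between immunogenicity endpoints and efficacy/safety assessments, states: "The following safety/efficacy assessments will be summarized by treatment-emergent AIA (Yes, No) and for each treatment group". For three kinds of hypoglycemia (any, severe, and documented symptomatic) the instruction reads: "the proportion of patients with at least one event will be compared between treatment groups using the same statistical model". The reference is to the hypoglycemia subgroup analyses of SAP 2.4.5.1. That model is a logistic regression on arm and HbA1c stratum, "with added fixed-effect terms for the subgroup and the subgroup-by-treatment interaction". Its named outputs are:

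- For the arm comparison: "Odds-ratios and 95% CIs will be presented across subgroups using forest plots"
- For the interaction term: "The significance level of the subgroup-by-treatment interaction will also be provided for descriptive purpose"

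The grouping variable comes from samples taken on treatment. Induced cases are "patients with at least one positive AIA sample at any time during the on-treatment period", among those without AIA or with a missing sample at baseline. Boosted cases are "patients with at least one AIA sample with at least a 4-fold increase in titers compared to baseline value at any time", among those with pre-existing AIA (SAP 2.1.4).

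The other outcomes in that part of SAP 2.4.6.1 (adverse events, injection site and hypersensitivity reactions, HbA1c, insulin dose) are described by AIA status and arm without a model. Peak titer is also plotted against outcomes, including hypoglycemia rate.

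**The concern.** There are two separate problems, both confined to the modelled hypoglycemia comparison.

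**Comparability.** Treatment-emergent AIA status is known only after treatment starts. Protocol 2.1 and 4.2 raise the possibility that switching primes the immune system, so the arm may influence who falls into AIA Yes. Within AIA Yes, or within AIA No, the two arms are then no longer the groups that randomization made comparable.

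**Target.** The objective concerns what AIAs do. The named odds ratios concern what the arm does among patients with a given AIA status. A reader looking for an estimate of the AIA–hypoglycemia association, with its uncertainty, will not find one among the planned outputs.

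At stake is the interpretation of one exploratory analysis. A within-group arm difference could be read as an effect of switching, or a set of null arm odds ratios could be read as evidence that AIAs do not matter.

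**Working it through.** **Inputs.** The documents give 73 PK-evaluable patients per arm as a minimum and about 184 randomized, so 92 per arm (SAP 1.3). That calculation reproduces: with a log-scale SD of 0.35, two one-sided tests at 0.05 and 73 per arm, power is 90.3% at a true ratio of 0.95 and 91.0% at 1.05. It concerns the PK endpoints only. The documents give no AIA rate and no hypoglycemia rate, so those below are assumptions.

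**1. What the named outputs measure.** Write the SAP model as

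logit P(event) = b0 + b1·arm + b2·stratum + b3·AIA + b4·arm×AIA

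| Quantity | Expression | Named as output? |
|---|---|---|
| Arm odds ratio in AIA No | exp(b1) | yes |
| Arm odds ratio in AIA Yes | exp(b1 + b4) | yes |
| Interaction | exp(b4) | p-value |
| AIA odds ratio, non-switching | exp(b3) | no |
| AIA odds ratio, switching | exp(b3 + b4) | no |

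Suppose AIAs raise hypoglycemia equally in both arms and arm has no other effect. Then b1 = b4 = 0 and b3 > 0. Both arm odds ratios are 1 and the interaction is null, whatever the size of b3. The AIA term is in the model but is not named for reporting.

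**2. Whether the arm contrast can mislead.** This is a large-sample simulation with 4 million patients per scenario. One unmeasured standard-normal trait raises the log odds of both AIA emergence and hypoglycemia by the same amount (0.5, 1.0 or 1.5). The hypoglycemia rate is 60%. Neither arm nor AIA affects hypoglycemia, so every true effect is an odds ratio of 1.

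| AIA incidence, non-switching / switching | Arm OR in AIA Yes | Arm OR in AIA No | Crude AIA Yes-vs-No OR |
|---|---|---|---|
| 15% / 15% | 1.00, 1.00, 1.01 | 1.00, 1.00, 1.00 | 1.3, 2.1, 3.9 |
| 10% / 20% | 0.97, 0.91, 0.81 | 0.98, 0.93, 0.90 | 1.2, 2.1, 3.8 |
| 10% / 30% | 0.95, 0.83, 0.68 | 0.96, 0.88, 0.80 | 1.2, 2.0, 3.4 |

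Each cell lists the three trait strengths in order. The arm odds ratio not conditioned on AIA is 1.00 throughout. Distortion of the arm contrast appears only when AIA incidence differs between arms. The crude AIA contrast is confounded in every row.

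**3. Precision.** Assume AIA incidence of 10%–20% and an event proportion q of 50%–80%, equal across groups, with no covariate adjustment.

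AIA-Yes patients per arm: 73 × 0.10 = 7.3 to 92 × 0.20 = 18.4.

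Arm odds ratio within AIA Yes, SE = √(2 / [n·q(1−q)]):
- n = 7.3, q = 0.8: √(2/1.168) = 1.309; exp(1.96 × 1.309) ≈ 13
- n = 18.4, q = 0.5: √(2/4.6) = 0.659; exp(1.96 × 0.659) ≈ 3.6

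AIA Yes versus No pooled over arms, SE = √([1/n₁ + 1/n₀] / [q(1−q)]):
- n₁ = 14.6, n₀ = 131.4, q = 0.8: SE = 0.690; factor ≈ 3.9
- n₁ = 36.8, n₀ = 147.2, q = 0.5: SE = 0.369; factor ≈ 2.1

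The 95% CI is the estimate divided and multiplied by the factor. The pooled AIA contrast is tighter, but the small AIA-Yes group still limits it.

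**The case against.** **The objective can be read as comparative.** It speaks of comparing clinical effects, in a trial about whether switching adds risk. On that reading the interaction is relevant, because exp(b4) is the ratio of the AIA odds ratios in the two arms. This stands as a reason to keep the between-arm results. It does not remove the gap: the two AIA odds ratios whose ratio is taken are not themselves reported.

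**The association is already visible.** Hypoglycemia proportions by AIA status and arm, titer scatter-plots, listings for titer outliers, and committee adjudication of possible AIA effects on glycemic control are all planned. This stands. A reader might infer that the plan cannot show any link between AIAs and hypoglycemia, but the documents do not support that. What is missing is an estimate with a CI.

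**The bias is conditional.** With equal AIA incidence the arm contrast is essentially undistorted, and Protocol 2.3 expects no meaningful immunogenicity difference. This stands. One cannot say that the within-group odds ratios will be biased, only that randomization does not protect them. The overall arm odds ratio in SAP 2.4.5.1, which is not conditioned on AIA, will be available beside them.

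**The AIA contrast is itself observational.** This stands in full. In the illustration its crude value strays further from 1 than the arm contrast does. It is preferable because it addresses the stated question, not because it is free of bias.

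**Counting only events after the Week 8 sample** may look like an obvious timing repair. It is not clearly better. AIA can first be detected at Week 12 or 16, so later events can still precede it. Protocol 4.2 expects antibodies within about 2 weeks of first exposure, so relevant events between Weeks 4 and 8 would be lost.

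**Conclusion.** The point holds as a minor one, for hypoglycemia only. The modelled outputs are arm odds ratios within a post-randomization grouping plus an interaction test. They do not estimate the AIA–hypoglycemia association, and a common AIA effect in both arms would leave them null. That conclusion follows from the model and needs no numerical assumption. The distortion figures and CI widths rest on assumed AIA and hypoglycemia rates.

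A reader might infer three wider claims that the documents do not support:

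- That every outcome in this part of SAP 2.4.6.1 is compared this way. Only hypoglycemia is modelled; the rest are descriptive.
- That a model meant for baseline subgroups was misapplied. SAP 2.4.5.1 built it for COVID-19 impact, which SAP 2.2 defines by events during the study.
- That the trial's conclusions are at risk. The objective is tertiary, SAP 2.4.6.1 labels the immunogenicity analyses descriptive without formal testing, and no primary or secondary conclusion depends on these odds ratios.

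**What to change.** In SAP 2.4.6.1, name the AIA Yes-versus-No odds ratio with 95% CI as the estimate for this objective for each hypoglycemia category. Report it pooled over arms and also by arm. Take it from the planned logistic model, with baseline AIA status added to arm and HbA1c stratum. State how a missing baseline AIA sample is classed, since such patients count as treatment-induced if later positive. Label the result an observational association.

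Keep the between-arm results within AIA groups as descriptive only, with a note that the grouping is determined after randomization and that the arms within each group need not be comparable.

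The cost is one added covariate and a different contrast from a model already planned, with no new data. The downside is that the estimate will be confounded to an unknown degree and imprecise if few patients become AIA positive. Severe hypoglycemia may be too sparse to model. The stated fallback of removing the stratum does not cure empty AIA-by-arm cells, and counts may then be all that can be shown.
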